## **G.** Adverse Event Monitoring

#### **G.1. Definitions**

Define adverse events (AEs), serious adverse events (SAEs), and unanticipated problems (UPs) for your study:  $\boxtimes$  N/A, no physical risks are anticipated with this research study, and we will use the definitions in the Tufts Health Sciences IRB's Reportable New Information policy.

## **G.2. Reporting Procedures**

- 1. Describe the protocol-specific reporting procedures, including who will be responsible for each step (e.g., PI, Data Coordinating Center, Medical Monitor), which forms should be completed, timeframes for reporting, how reports will be distributed, and what follow-up is required:

  We will comply with FDA requirements for records and reports (21 CFR §812.140, 21 CFR §812.150).
- 2. *Include specific details of reporting procedures for:* 
  - a. *Deaths, life-threatening events, pregnancies:* Deaths and life-threatening events that meet specified categories in RNI policy will be reported using eIRB (Report New Information button) within 5 business days.
  - b. *Other SAEs*: SAE's that meet specified categories in RNI policy will be reported using eIRB (Report New Information button) within 5 business days.
  - c. *Other AEs:* AE's that meet specified categories in RNI policy will be reported using eIRB (Report New Information button) within 5 business days.
  - d. *Other UPs:* UP's that meet specified categories in RNI policy will be reported using eIRB (Report New Information button) within 5 business days.

## **G.3.** Reportable New Information

☑ Check to confirm that reportable new information will be reported to the IRB per the Tufts Health Sciences IRB's Reportable New Information policy.

#### **H. Statistical Considerations**

#### **H.1. Study Endpoints**

- 1. Describe the primary and secondary study endpoints: GI luminal content and stool microbial composition.
- 2. Describe any primary or secondary safety endpoints: Recovery of the 12 mini-pills.

#### H.2. Sample Size

- 1. Specify the number of subjects to be enrolled in total across all sites: 60
- 2. Specify the maximum number of subjects to be enrolled at the Tufts site(s). Subjects who sign an ICF are considered "enrolled". For studies that have a separate screening ICF, this number is the number of subjects who sign a screening ICF: 60
  - a. Specify the number of subjects expected to be enrolled at the Tufts site (i.e. sign the screening or study ICF): 60
  - b. Estimate the minimum number of subjects needed to **complete** the study at the Tufts site(s): 30
  - c. Provide the rationale for enrolling this number of subjects at the Tufts site: Based on our sample size calculation, we need 30 subjects (aiming for 15 postmenopausal women, 15 older men) to complete both diet phases, and have analyzable data. To account for potential drop-outs, and based on our prior experience with conducting dietary interventions, enrolling 60 participants should allow us to meet our target.
  - d. *If a large number of withdrawals and/or dropouts is expected, explain why:* We have estimated the number of drop-outs expected based upon prior dietary intervention studies

Tufts Health Sciences IRB Protocol Template

<sup>2 If Tufts IRB is requested to be the Single IRB of Record for external sites (as per section K.3 Multi-Site Research), include all sites in these enrollment numbers.

performed at the HNRCA. We have considered the time commitment for the various study components as well as the accounted for participants who inevitably have unavoidable unrelated issues that may cause them to stop participation (e.g., moving to another location, schedule change and altered availability for participating).

3. Provide a sample size justification: Based on microbiota β diversity values obtained from samples collected from hounds, the UniFrac distance between small intestine and stool averages 0.4 distance units with a SD of 0.05. Using these estimates, and assuming similar values apply to humans, a power ≈1 will be achieved with 10 clinical trial participants/group assuming α = 0.05. Data dispersion in human participants may well exceed what we observe in hounds. The power calculation based on double the SD returns power of 0.93 for the same n of 10. Since the clinical trial uses a crossover design, UniFrac distances will be obtained from intra-individual comparisons, likely reducing 16S data variability compared to inter-individual distances. In relation to diet, power calculations are tentative because data on the effect of diet on human GI microbiota other than microbiota in stool are rare. Hence, a sample size of 30 (15 male, 15 female) is assumed to be adequate.

## **H.3. Statistical Analyses**

1. Describe the statistical analyses that will be performed for this study: Microbiota taxonomic profiles across GI locations will be characterized using standard diversity measures as well as relative abundances of specific taxa. Alpha diversity and beta diversity measures will be compared across regions using repeated measures ANOVA to account for multiple samples from the same individual. Effects of a plant-based and meat diet on GI tract microbiota will be compared, by region, using zero-inflated Gaussian mixed models, implemented in the R package "glmmTMB". These models can include fixed and random effects to account for dependencies from the crossover design, and evaluate sequence and period effects on the microbiota taxonomic profiles. To compare the effect of the of the plant-based and meat diets on cardiometabolic risk factors, absolute values at the end of each diet phase and change from baseline to 2 weeks after randomization will be compared using a two sample t-test or Wilcoxon Rank Sum test.

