## Specific aims:

- 1. To assess the feasibility of sampling GI luminal content from targeted regions in humans using the mini-pill and recovering the sealed mini-pills post-elimination in the stool.
- 2. To analyze and compare the luminal content microbial population (microbiota) recovered from two GI regions and in stool, after consumption of diets differing in source of protein (meat and plant-based meat alternatives).

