#### Exploratory aim:

To compare the effects of diets containing meat and plant-based meat alternatives on metabolites in stool and blood biomarkers associated with cardiometabolic risk.

The ingestible mini-pill is a non-invasive, single-use, passive collection device that is not intended for diagnosis or treatment. The mini-pills have already been developed, tested and validated by two Tufts researchers, Drs. [name] (School of Engineering) and [name] (School of Veterinary Medicine), *in vitro*, *ex vitro*, and *in vivo* in animal models (*Supplement 1: Research Strategy and Supplement 2: Soft Autonomous Ingestible Device for Sampling the Small Intestinal Microbiome, Del-Rio-Ruiz R et al.*, *manuscript in review*). A NSR device designation is being sought from the IRB to conduct a 2-phase randomized-controlled double blind crossover trial in humans by providing two entrées per day containing either meat or plant-based meat alternatives for up to 3 weeks each. After 2 weeks on each diet, participants will consume a provided breakfast meal and then be asked to swallow 6 mini-pills along with a blue food coloring dissolved in 50 mL of water, return home and collect stool samples until all the mini-pills are recovered (varies between 2 and 4 days, but can be up to 6 days). This protocol will allow us to describe the diet-induced progressive change in the GI tract microbiota prior to and including that in the stool.

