2. Rationale for the research and preliminary data: The mini-pill development and subsequent validation work was funded through a NIH R21 phased innovation mechanism. NIH R33 funding for the second phase, the proposed human trial, was contingent on successful completion of the *in vitro*, *ex vivo* and *in vivo* work in pigs and hounds. As part of the R21 phase of the proposal, we have successfully validated a 3D-printed sampling device, referred to as a *mini-pill*, to retrieve luminal content at pre-determined regions of the GI tract in pigs and hounds (*See Supplement 2: Soft Autonomous Ingestible Device for Sampling the Small Intestinal Microbiome, Del-Rio-Ruiz R et al., in review*).

The proposed study includes ingestion of six mini-pills per diet phase, three targeted to collect lumenal content from the upper GI, tract and three targeted to collect lumenal content from lower down in the GI tract. The rationale for three pills per location is to establish that sufficient qunatity of representative luninal content at each site is collected, and to determine reproducability. Sampling relies on uptake of intestinal content through the side inlets of the empty mini-pill as a result of natural GI peristalsis. Regional sampling of the mini-pill is initiated upon dissolution of the pH-sensitive enteric coating. Because the pH of the GI tract increases as the luminal content progresses from the duodenum to the colon, different pH-sensitive enteric material can be used to coat the mini-pills to sampling differ regions of the GI tract. Critical to minimizing contamination from downstream material, embedded absorbent beads located inside the mini-pill activate a valve which closes the intake inlet through which the sample has been acquired. (See Supplement 3: Minipill for Collection of GI Tract Luminal Content).

3. Significance of the research objectives: Because regions of the GI tract differ with respect to oxygen tension, pH and nutrient availability, the commonly sampled microbiota in stool is unlikely to reflect the microbial communities populating more proximal regions of the GI tract, particularly, the small intestine. To gain insights into the impact of the entire GI tract microbial environment on health and disease, it is essential to develop a methold to non-invasively sample luminal content from targeted locations, particularly upstream of the colon.

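### Repeated-measures ANOVA is named for beta diversity across regions with no response defined; on the per-pair or per-region distances it could use, it does not directly test whether composition differs between regions

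*Protocol*

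**What the plan says.** One sentence in Protocol H.3 covers both kinds of diversity: "Alpha diversity and beta diversity measures will be compared across regions using repeated measures ANOVA to account for multiple samples from the same individual". It gives no response variable for beta diversity.

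What beta diversity means here is found in H.2, item 3. In hounds, "the UniFrac distance between small intestine and stool averages 0.4 distance units with a SD of 0.05", and in the trial "UniFrac distances will be obtained from intra-individual comparisons".

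The question to be answered is Aim 2 in B.1: "To analyze and compare the luminal content microbial population (microbiota) recovered from two GI regions and in stool", under the two diets. H.1 gives the endpoint as "GI luminal content and stool microbial composition".

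The rest of H.3 adds no other test between regions. "Microbiota taxonomic profiles across GI locations will be characterized using standard diversity measures as well as relative abundances of specific taxa" is descriptive, and the glmmTMB models compare the two diets within each region.

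On the expected pattern, B.1 speaks of a "diet-induced progressive change in the GI tract microbiota prior to and including that in the stool". B.2 explains the coatings by the fact that "the pH of the GI tract increases as the luminal content progresses from the duodenum to the colon". Both suggest a gradient; neither gives its size in humans. B.2 also provides three mini-pills per location in each phase, so replicates exist.

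**The concern.** A repeated-measures ANOVA across regions needs a number for each participant in each region. Alpha diversity supplies it. A distance belongs to two samples, so a region gets a distance value only if one is built for it, from its replicate pills or from a centroid, and such a value describes how spread out the region is. The alternative is to let the region pairs be the levels of the factor, which changes the hypothesis.

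The only inferential comparison of composition between regions could therefore answer a different question. It could miss a real regional difference, or report one when a single site is merely more variable.

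**Working it through.** **The plan's own figure.** H.2 gives a distance of 0.4, SD 0.05, 10 per group and alpha 0.05. With a two-sided two-sample normal test, power = Φ(0.4 / (SD × √(2/10)) − 1.96).
- SD 0.05: 0.4 / 0.0224 = 17.9, power ≈ 1. This reproduces.
- SD 0.10: 0.4 / 0.0447 = 8.94, power above 0.9999, not the stated 0.93. That mismatch is a separate matter and is not used below.

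The calculation does not supply the missing response either. A distance is positive even when regions do not differ. In the compositional simulation described below, its mean was 0.23 with no regional difference, and a test of it against zero rejected 100% of the time.

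**What each response tests.** Let region r have mean profile μ_r and residual SD s_r in each of D dimensions (Euclidean approximation).
- Region pair (i, j), within person: E[d²] = ‖μ_i − μ_j‖² + D(s_i² + s_j²). The ANOVA null is that the three pair distances are equal.
- Within-region replicates: E[w²] = 2D·s_r². There is no μ term, so the null is equal spread.
- Distance to a region centroid: the mean is removed, so again the null is equal spread.
- Aim 2 asks whether μ_upper = μ_lower = μ_stool.

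With D = 10 and s = 1, the expected squared distances (upper-lower, upper-stool, lower-stool) are:
- all pairs separated by Δ: 20 + Δ² each, so the pairwise null is true although the regions differ;
- stool shifted by 1.41: 20, 22, 22;
- stool unshifted but 1.3 times as dispersed: 20, 10(1 + 1.69) = 26.9, 26.9.

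The last two show the same pattern, one shorter and two longer distances. Simulated mean distances agree: 4.36, 4.57, 4.57 and 4.36, 5.05, 5.06.

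**Simulation.** Assumptions: 30 participants (the H.2 target), 3 samples per region, 2 phases, 10-dimensional Euclidean stand-in for UniFrac, participant SD 1, residual SD 1, shift 1.41, 199 permutations, 1000 trials per scenario (Monte Carlo error about 1.4 points at 5% and 3 points at 50%). Rejection at 5%, in percent:

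| Scenario | Pairwise ANOVA | Centroid ANOVA | Permutation within participant |
|---|---|---|---|
| No shift | 7 | 6 | 5 |
| Equal separations | 4 | 6 | 100 |
| One region shifted | 87 | 5 | 100 |
| Gradient 2.82 SD | 100 | 5 | 100 |
| Gradient 1.41 SD | 62 | 5 | 100 |
| Spread only (1.3×) | 100 | 100 | 6 |

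A 300-run repeat that added within-region distances gave 5 to 7% for all three ANOVA forms under equal separations (permutation 100%), and 100% for all three under unequal spread (permutation 4%).

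**Dependence on gradient size** (percent):

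| End-to-end gradient (SD) | 0.7 | 1.0 | 1.41 | 2.0 | 2.82 |
|---|---|---|---|---|---|
| Pairwise, full design | 9 | 21 | 62 | 99 | 100 |
| Pairwise, one sample and one phase | 6 | 5 | 10 | 26 | 72 |
| Permutation, one sample and one phase | 30 | 59 | 94 | 100 | 100 |

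Permutation in the full design gave 99.5 to 100 throughout.

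**Check on compositional data.** Using 30-taxon log-normal compositions with Bray-Curtis distance, 30 participants and one phase, equal separations at a mean distance of about 0.42 gave 5% for both pairwise and within-region ANOVA, against 100% for permutation. Unequal spread alone gave 100% for both ANOVA forms and 16% for permutation. Unequal separations gave 100% for pairwise ANOVA and 7% for within-region ANOVA. The pattern does not depend on the Euclidean stand-in.

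**The case against.** The strongest reply is that H.3 leaves the response open, that a statistical analysis plan may define it, and that some definitions would work.

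- *Ordination scores.* ANOVA on two principal-coordinate axes rejected 92 to 100% in the four scenarios with a regional shift, and 5% under spread only. It covers only the chosen axes, though. When participants differed by SD 3 on two axes unrelated to region, it fell to 31% (equal separations), 25% (one region shifted) and 58% (gradient 2.82 SD), with permutation still at 100%.
- *Between-region against within-region distances.* The replicate pills and the within-person distances of H.2 lend this some support. It rejected 99.9% under equal separations, 96% with one region shifted, 78% for a 1.41 SD gradient and 9% under spread only. But it contrasts two kinds of distance, not regions. It also rejected 100% with no common shift when participant-by-region differences (SD 0.5) persisted over phases.

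It stands that either response would bear on separation. The text names neither. H.3 is also not silent on the matter: it commits to a method across regions.

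Four further points stand. The protocol expects a gradient, and a large one costs the pairwise form nothing. Every effect size is assumed; the 1.41 SD gradient moves mean distances only from 4.36 to 4.42, 4.57 and 4.41, less than 5%. The centroid form has little support in the text, since H.2 speaks of distances within a person; the within-region form fits that better but also measures only spread. And PERMANOVA is not immune to unequal spread, as the 16% above shows.

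**Conclusion.** The point holds in a limited form. H.3 fixes repeated-measures ANOVA for beta diversity across regions without a response. With distances per region pair it tests equality of the pair distances; with within-region or to-centroid distances it tests equality of spread. Neither directly tests Aim 2 or the composition endpoint, and both react to spread alone. This conclusion follows from the hypotheses and needs no effect size.

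The size of any power loss does depend on assumptions: none for a large gradient, some for a moderate one, and rejection at about the nominal 5% if the regions are equally separated.

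A reader might infer more: that a region can have no beta-diversity value at all, that no repeated-measures ANOVA on UniFrac distances can detect regional separation, or that this trial has about 5% power for Aim 2. The documents do not support these. Replicate pills do give each region a within-region distance; the two responses discussed under the objection can detect separation; and the protocol points to a gradient while giving neither a human effect size nor a within-region baseline distance.

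The change should be made because it concerns a specific aim and is cheap. This remains a proof-of-concept study whose first aim is feasibility, and the sequencing data are unaffected.

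**What to change.** In H.3, keep repeated-measures ANOVA (or a mixed model) for alpha diversity only. For beta diversity write, for example:

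> Regional differences in composition will be tested on the UniFrac matrix by PERMANOVA. Replicate samples of a region are averaged in principal-coordinate space, or kept as one block, per participant and phase. Region labels are permuted within participant, with the same permutation in both diet phases. A dispersion test is reported alongside.

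The permutation unit has to be stated. With no common shift but a participant-by-region SD of 0.5 persisting over phases, this scheme rejected 4.3%, blocks permuted independently in each phase 32.5%, and single samples permuted freely 77.9%.

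The cost is wording and a standard permutation routine on the same data. There are small downsides. The blocks must be specified. Unrecovered pills and varying stool numbers make block sizes unequal, which averaging avoids. And because PERMANOVA can react somewhat to unequal spread, it must be read together with the dispersion test.

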# C.4. Withdrawal of Subjects

- 1. Describe anticipated circumstances under which subjects will be withdrawn from the research without their consent: Non-compliance with study protocol based on not attending pre-scheduled study visits, not providing blood or stool samples, not picking up and consuming provided study entrées, change in medical status or use of steroids or oral antibiotics during the study. Additionally, if a subject does not follow all of the HNRCA volunteer rules and regulations, they will be withdrawn from the study without their consent.
- 2. Describe procedures that will be followed when subjects either withdraw voluntarily or are withdrawn from the research, including the possibility of partial withdrawal from study intervention with continued data collection. If a participant wishes to withdraw part-way through the study they are at liberty to do and no further data will be collected. Samples and data that have already been collected will be analyzed as per protocol.
- 3. Describe any necessary safety precautions to be applied to subjects who withdraw or are withdrawn (tapering drug doses, evaluative x-ray, etc.):  $\boxtimes N/A$

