#### E.2. Procedures

1. Summarize the research design and sequentially identify all procedures to be performed to accomplish the specific aims of the project.: Participants meeting the eligibility criteria will be randomly assigned to one of two randomization sequences (Phase I and Phase II), the meat or plant-based meat alternative entrées, or vis versa, to achieve a crossover design. There will be a 2-week washout period between the phases.

During each diet phase, participants will be provided with 2 study entrées per day and counseled by the research dietitian to consume them at two different times during the day. The length of each diet phase will be ~3 weeks (i) 2 weeks of meat or plant-based meat alternative entrées, (ii) ingestion of the mini-pills on week 2 (day 14), and week 5 (day 49) of the diet phases, and (iii) additional 2 to up to 6 days (consuming 2 entrées/day) until the mini-pills are recovered from the stool. In humans, prior work has established the adequacy of the intervention period to affect microbial communities. A prior study in humans using a similar device indicated that all devices were recovered in stool using a collection window between 6 and 48 hours. The mini-pill recovery window in our study using pigs and hounds was up to 72 hours. We plan to use the appearance of blue dye in the stool to better tailor the stool collection window for our participants.

Table 1: Summar	v of Study	Timeline and	l Procedures
Table 1. Sallilla	, or braay	I IIII CIIII C WIIC	1 1 0 C C G G I C D

Study Procedures	Diet Phase I		Wash out		Diet Phase II			Total #	
Study weeks (days)	1 (1-7)	2 (8-14)	3 (15-21)	4 (22-28)	5 (29-35)	6 (36-42)	7 (43-49)	8 (50-56)	8 (56)
Food pick up	X	X	X			X	X	X	6
Entrée check list return		X	X				X	X	4
Weight	X	X				X	X		4
Waist circumference	X	X				X	X		4
Blood pressure	X	X				X	X		4
Fasting blood samples*	X	X				X	X		4
Mini-pill ingestion		X					X		2
Stool collection/return**			XXX					XXX	up to 6
Diet 24-hr recalls	X	XX					XX		5
Payment			X					X	2

\*Blood will be drawn in the morning after an overnight fast (8 to 10 hours, no food or drink except water and approved medications). The amount drawn on days 1, 14, 36 and 49 will be 12 mL (about 1 tablespoon) for a total of 48 mL over the entire study (about 4 tablespoons).

#### Diet Phase 1

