Week 1\_Day 1: Following the screening visit, participants will come to the HNRCA after an 8 to 10 hour fast to return their stool sample. They will then be given the opportunity to review and sign the Study Informed Consent form and also be given the option to review and sign the Optional Tissue Banking Informed Consent form. Once enrolled, participants will have their weight, waist circumference, and blood pressure measured and provide a fasting blood sample. They will meet with a registered dietician to review instructions for entrée storage/consumption and pick up diet phase I specific entrées and checklist.

Week 2\_ Day 8: Participants will come to the HNRCA to pick up another week of study entrées and also return and review their Entrée Checklist with a registered dietician.

*Week 2-Day 14:* Participants will come to the HNRCA after an 8 to 10 hour fast to provide a fasting blood draw. They will be given a breakfast containing a study entrée specific to the diet phase to be consumed within 30 minutes, and then asked to swallow 6 mini-pills along with blue dye dispersed in ½

\*\*The number of stool samples to be collected will vary depending on mini-pill recovery

cup of water within 15 minutes. Additional water may be consumed, if desired. Participants will be given study entrées for another week and stool collection kits with cooler and instructions.

*Week 3-Days 15 to 21:* Participants will continue to consume 2 entrées per day until the mini-pills are eliminated in the stool, which can vary between 2 and 4 days, but can be up to 6 days. Participants will be asked to collect and return all stool samples produced every 48 hours, until they are informed by study staff that all pills have been recovered.

Participants can stop consuming the entrées once all mini-pills are recovered. There will be a 2 week break at this point during which participants will have no study obligations and can consume their normal diet. If all of the mini-pills are not recovered after 6 days, participants can stop consuming the study entrees, and we will conduct a 2-week follow up telephone call to inquire about symptoms or concerns.

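### Repeated measures ANOVA is a weak choice for the region comparison: its classical form drops participants with an empty region and assumes sphericity, while mixed models are already planned for diet

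*Protocol*

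**What the plan says.** Section H.3 sets the method for the region part of Aim 2: "Alpha diversity and beta diversity measures will be compared across regions using repeated measures ANOVA to account for multiple samples from the same individual". It does not say whether phase enters as a second within-subject factor, and it states no rule for an empty region. For the diet comparison, the next sentence turns to zero-inflated Gaussian mixed models, with fixed and random effects for the crossover structure.

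Other sections bear on how complete the data will be:

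- B.1 makes sampling from targeted regions and recovery of the pills a feasibility aim.
- B.2: "The proposed study includes ingestion of six mini-pills per diet phase", three for each of two locations. Part of the reason for three is "to establish that sufficient qunatity of representative luninal content at each site is collected"; the other part is reproducibility.
- E.2 has a provision for both phases that begins "If all of the mini-pills are not recovered after 6 days". It also reports: "A prior study in humans using a similar device indicated that all devices were recovered in stool".
- C.4, on participants who withdraw: "Samples and data that have already been collected will be analyzed as per protocol".
- C.5.3 and H.2 allow 60 to be enrolled so that 30 complete both phases with analyzable data.

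**The concern.** Each full participant supplies upper pill, lower pill and stool under two diets. Classical repeated measures ANOVA works on a complete within-subject layout, so a participant with an empty region leaves the analysis entirely, including the regions that were sampled. In a first human use of the device, where recovery is itself under study, an empty region is foreseeable. Completeness may also depend on transit, because a slow pill is more likely to miss the collection window. The complete cases would then be a selected group.

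The second issue is sphericity: the variances of all pairwise region differences are assumed equal. Two luminal samples from the same kind of device and one stool sample are unlikely to satisfy that, and H.3 names no correction.

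At stake are precision, representativeness and, to a small degree, the error rate of the Aim 2 region comparison.

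**Working it through.** **Plan's own figure.** The protocol gives no failure rate and no expected number of complete participants, so there is none to reproduce. The power statement in H.2 concerns a UniFrac distance with 10 per group and does not address missing cells.

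**Inputs.** From the protocol: 30 completers, 3 regions, 2 phases, 3 pills per location per phase. Assumed: per-pill failure f, or cell usability q, where a cell is one location in one phase. Stool is taken as always present.

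**1. What the classical test does with one empty cell.** Simulated data for 30 participants x 3 regions x 2 phases give 180 cells. One cell was deleted.
- Region and phase both within-subject: the standard routine rejects the data as unbalanced. The participant must be dropped, leaving 29 of 30.
- Region only, averaged over phase: it runs on all 30, with error df (30 - 1) x (3 - 1) = 58.
- Mixed model: all 30 participants and 179 observations are kept.

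**2. Expected complete participants, independent pill failures, one usable pill enough.** A cell is empty with probability f³. With four pill cells the expected number complete is 30 x (1 - f³)⁴.
- f = 0.10: 30 x 0.999⁴ = 29.9
- f = 0.20: 30 x 0.992⁴ = 29.1
- f = 0.30: 30 x 0.973⁴ = 26.9

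**3. Expected complete participants for a given cell usability q, phase in the layout.** 30 x q⁴, with cells independent.
- q = 0.95: 24.4
- q = 0.90: 19.7
- q = 0.80: 12.3

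If the pills in a cell failed independently, these q would need f = (1 - q)^(1/3) = 0.37, 0.46 and 0.58. At modest per-pill failure rates, such q arise only if the pills of a location fail together.

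**4. Same q, region only, averaged over phase.** A participant is lost only if a location is empty in both phases: 30 x (1 - (1 - q)²)².
- q = 0.95, 0.90, 0.80: 29.9, 29.4, 27.6

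The loss is small, but where a cell is missing that region's mean rests on one diet while the others average two.

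**5. Sphericity.** Simulated rejection rates at nominal 5%, n = 30, three levels, covariances assumed:
- compound symmetry: 0.051
- epsilon 0.75: 0.065
- epsilon 0.69 to 0.71: 0.067 to 0.068
- epsilon 0.69 with Greenhouse-Geisser correction: 0.052

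**The case against.** The strongest reply is that the protocol nowhere says incomplete participants will be discarded. It names a method and its purpose; layout and handling of empty cells can be left to an SAP, and the term is sometimes used loosely for a mixed-model fit. That is fair as to detail. However, the method is a stated choice, and the same section says mixed models when it means them. If a mixed model was intended, the change only clarifies.

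Three stronger readings are tempting, and the documents do not support them:

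- **That every one-phase participant is lost, contradicting C.4.** The sentence names region only. Averaged over phases, a one-phase participant is kept. The conflict arises only if phase is also a within-subject factor. H.2 in any case defines the target as completers of both phases.
- **That the trial expects unrecovered or under-filled pills.** E.2 is conditional and cites full recovery with a similar device. The reason given for three pills implies that quantity is uncertain, but it predicts no shortfall, and the triplicate protects against an empty region.
- **That 24, 20 or 12 complete participants is the likely outcome.** Those figures need clustered failures. Clustering is plausible, since pills aimed at one location share a coating target and one person's pH and transit, but nothing in the protocol demonstrates it.

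It is also true that a mixed model is not automatically better. On complete data, a random-intercept model with common residual variance gives the same region F as the ANOVA whenever the participant variance estimate is positive, so it has the same sphericity problem. With a participant intercept alone, up to three pills from one location and phase would count as independent. Both objections stand and shape the fix.

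**Conclusion.** The point holds at moderate strength. H.3 fixes, for the region comparison, a method that in its classical form is complete-case and assumes sphericity, while the same section applies mixed models to the same samples for diet. Replacing it is worthwhile and nearly free.

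The demonstrated cost is conditional. With independent failures of up to 20% per pill, about one participant in 30 is lost. The loss becomes serious (24, 20 or 12 of 30 remaining) only with clustered failures, phase in the layout, and the assumed usabilities. The error-rate inflation is about 1.5 to 2 percentage points at epsilon near 0.7, under assumed covariances, and a routine correction would also remove it. Selection on transit is plausible but cannot be sized from the protocol.

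**What to change.** In H.3, replace repeated measures ANOVA with a linear mixed model fitted to all available samples, including those of one-phase participants:

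- **Fixed effects:** region, diet, period and sequence.
- **Random effects:** participant, and participant-by-phase-by-region so that replicate pills are not treated as independent. Alternatively, average the replicates within each cell first.
- **Variance:** residual variance allowed to differ by region. With averaged cells and three regions, this lets the variances of the pairwise differences differ, which a plain random intercept does not.
- **Beta diversity:** state the layout separately. Apply the model to within-participant between-region distances, with one value per participant, phase and region pair.

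The cost is a few sentences in H.3 and slightly more modelling work. Visits, procedures and sample size do not change, and the package already named for the diet models can fit this. One limitation should be stated: the model assumes that missingness is explained by observed data, so losses caused by transit will have less impact but are not fully repaired. Reporting the number of usable pills by location and phase alongside the analysis would let readers judge this.
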